6.2 Treatment Administration

Treatment will be administered on an outpatient basis. Reported adverse events and potential risks are described in Section 8.0. No investigational or commercial agents or therapies other than those described below may be administered with the intent to treat the patient's malignancy.

Dose-Escalation Schedule				
Dose Level	Dose of MGE			
Level 1	1 pill po BID			
Level 2	2 pills po BID			
Level 3	3 pills po BID			
Level 4	4 pills po BID			
Level 5	5 pills po BID			

6.2.1 Definition of Dose-Limiting Toxicity (DLT)

Dose-limiting toxicity (DLT) will be defined as grade 3 gastrointestinal side effects attributable to treatment or any grade 4 or 5 adverse event attributable to treatment as per the Common Terminology Criteria for Adverse Events (CTCAE) 4.0 criteria. Any adverse event attributable to treatment and resulting in permanent discontinuation of MGE will be considered a DLT. Toxicity will be assessed at 4 weeks. Any DLTs that occur 1 day (day 29) after the 4 week period will be evaluated and considered as potentially attributable to the administration of MGE during the first 4 weeks. The washout period for this drug is 24 hours. Dose escalation will proceed within each cohort as follows:

Number of Patients with DLT at a Given Dose Level	Escalation Decision Rule		
0 out of 3	Enter 3 patients at the next dose level.		
> 2	Dose escalation will be stopped. This dose level will be declared the maximally administered dose (highest dose administered). Three (3) additional patients will be entered at the next lowest dose level if only 3 patients were treated previously at that dose.		
1 out of 3	 Enter at least 3 more patients at this dose level. If 0 of these 3 patients experiences DLT, proceed to the next dose level. If 1 or more of this group suffer DLT, then dose escalation is stopped, and this dose is declared the maximally administered dose. Three (3) additional patients will be entered at the next lowest dose level if only 3 patients were treated previously at that dose. 		
≤1 out of 6 at highest dose level below the maximally administered dose	This is generally the recommended phase 2 dose (Maximum Tolerated Dose [MTD]). At least 6 patients must be entered at the recommended phase 2 dose.		

6.2.2 Dose modification in the event of toxicity

In the event of dose-limiting toxicity, the patient will be removed from the study and the escalation decision rules defined above will be followed. There will be no dose-modifications on study. Either the patient or the treating physician can chose to discontinue MGE at any time. If necessary, MGE can be held for up to 7 days in the first month and for up to 21 days subsequently, as described in Section 6.5.1.

6.3 Study procedures

6.3.1 Recruitment

- 6.3.1.1 Potentially eligible patients will be recruited from the Wake Forest Comprehensive Cancer Center
- 6.3.1.2 The research nurse (RN) will be contacted to review eligibility and to consent eligible patients in person.
- 6.3.1.3 The RN will obtain baseline surveys, clinical information and ensure research labs are drawn and processed per protocol. Pill dairy will be provided at each visit.
- 6.3.1.4 Study drug (30-day supply) will be provided to participant by the RN.

6.3.2 Follow-up Assessments

- 6.3.2.1 Study coordinator will contact participants 2 weeks after each clinic visit until week 8 to assess medication adherence and ascertain any potential adverse events.
- 6.3.2.2 The RN will review AE with the patient at each follow-up visit in clinic, perform pill count, obtain clinical information per protocol and administer surveys at 4 and 8 weeks per protocol. RN will obtain study labs are each visit and provide 30-day supply of MGE at prescribed dose level.

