6.0 Treatment Plan

6.1 Study-Related Activities

Measures / Forms	Pre- Study ^a	Baseline	Week 2 ^h	Week 4 ^j	Week 8 ^k	Every 4 weeks ^k	Off-study
Informed consent	Х						
Demographics	Х						
Medical history	Х			Х	Х	Х	
Concurrent meds	Х			Х	Х	Х	
Physical exam	Х			Х	Х	Х	
Vital signs	Х			Х	Х	Х	
Weight		Х					
Height		Х					
ECOG Performance Status	Х			Х	Х	Х	
Pill Diary		Х		Х	Х	Xi	
Adherence assessment			Х	Х	Х		
Quality of life and fatigue assessments		х		х	Х	Х	
Tumor measurement by imaging ^b	Х				Х	Xp	
Tumor markers (if applicable) ^c		Х		Х	Х		
CBC w/diff, platelets	Х	Х		Х	Х	Х	
Serum chemistries ^d	Х	Х		Х	Х	Х	
B-HCG ^e	Х						
INR check ^f			Х				
Phenolic levels (blood and urine)		Х		Х	Х		
Research labs (cytokines and growth factors)		Х		х	х		
Adverse event evaluation		Х	Х	Х	Х	Х	
Vital status ^g							Х

^a Pre-study imaging listed in table must be completed **within** 42 days prior to registration. Additional pre-study activities need not be repeated if performed within 10 days of starting study drug.

^b CT imaging or other imaging modality will be obtained at baseline (within 42 days of registration) and at 8 weeks (± 7 days). Imaging will then be q12 weeks (± 28 days) for as long as the patient remains on study. CT, PET/CT, or MRI are acceptable imaging modalities and all imaging will be considered per standard of care for patients on active cancer treatments.

^c Tumor-specific markers may include but are not limited to testosterone level and PSA for prostate cancer patients, CEA for colorectal patients, and CA19-9 for pancreatic cancer patients as performed per standard of care.

^d Albumin, alkaline phosphatase, total bilirubin, bicarbonate, BUN, calcium, chloride, creatinine, glucose, potassium, total protein, SGOT[AST], SGPT[ALT], sodium.

^e Serum pregnancy test (women of childbearing potential).

^f Patients taking warfarin will have INR checked within 2 weeks of starting MGE. This can be performed locally.

^g Vital status will be assessed by chart review or phone every 6 weeks (± 14 days) after patient comes off study.

^h Phone contact will occur 2 weeks after each clinic visit (± 3 days) until the Week 8 visit is complete. ⁱ Patients will not be asked to complete a pill diary after 6 cycles (24 weeks).

^jWeek 4 study appointments will be scheduled at day 28 ±3 days.

^k Study appointments at Week 8 and after will be scheduled 28 days after the prior appointment, ± 7 days

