9.1 Drug Accountability

Drug accountability logs will be provided and maintained by the Wake Forest Investigational Drug Services for the investigative agent (MGE) used under this protocol. These logs shall record quantities of study drug received and quantities dispensed to patients, including lot number, date dispensed, patient identifier number, protocol number, dose, quantity returned, balance remaining, and the initials of the person dispensing the medication.

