10.0 Laboratory Studies

10.1 Phenolic assays

Total and component phenolics will be measured from blood and urine at baseline, 4 weeks, and 8 weeks if the patient remains on MGE. Blood assays will require approximately 10ml of blood. For the polyphenolic analysis²⁶ one tube of blood at each time point will be collected in tubes containing EDTA and ascorbic acid and stored at - 80°C for an indefinite period of time. The blood sample will be thawed on ice and used to measure polyphenols by ultra-high performance liquid chromatography (UPLC) coupled to mass spectroscopy detection (UPLC-MS).

A spot urine collection will be collected at baseline, 4 weeks, and 8 weeks if the patient remains on treatment with MGE. The urine will be collected into a urine collection cup and mixed with ascorbic acid; 20 mL aliquots will be stored at -80°C for an indefinite period of time. The urine will be thawed on ice and used to measure polyphenols by UPLC-MS.

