12.2 Analysis of Secondary Objective

12.2.1 To monitor toxicity at 4, 8, and every 4 weeks thereafter on MGE

To analyze objective 2.1.1, we will summarize any expected toxicities, any laboratory based toxicities, and any grade 3 or higher gastrointestinal toxicities and any grade 4 or higher toxicities using frequency tables overall and by week.

12.2.2 To evaluate change in phenolic levels (total and component, blood and urine) from baseline to 4 and 8 weeks

To analyze objective 2.2.2, we will fit a mixed model ANOVA model with phenolic level as the outcome and time (baseline, 4, and 8 weeks) as a fixed effect and subject as a random effect. We will use contrasts to estimate the changes from baseline to week 4 and week 8.

12.2.3 To evaluate change in serum cytokines and growth factors from baseline to 4 and 8 weeks on MGE

To analyze objective 2.2.3, we will fit a mixed model ANOVA model with the outcome of interest (cytokine or growth factor) as the outcome and time (baseline, 4, and 8 weeks) as a fixed effect and subject as a random effect.

We will use contrasts to estimate the changes from baseline to week 4 and week 8.

12.2.4 To observe the response rate of MGE in patients with metastatic cancer.

To analyze objective 2.2.4, we will characterize response at 8 weeks using frequency table. We will also characterize the best response at the end of treatment with MGE using a frequency table.

12.2.5 To assess overall and progression-free survival in patients with metastatic cancer receiving MGE.

To analyze objective 2.2.5, we will summarize overall survival and progression-free survival using the Kaplan-Meier method. We will calculate median survival rates and associated 95% confidence intervals. Patients will be censored at date of last contact.

12.2.6 To assess global quality of life and fatigue in cancer patients taking MGE.

Quality of Life and fatigue will be monitored every 4 weeks until the end of the study. To analyze objective 2.2.6, we will fit a mixed model ANOVA model with phenolic level as the outcome and time (baseline, every 4 weeks) as a fixed effect and subject as a random effect. We will use contrasts to estimate the changes from baseline to each follow-up time period.

12.2.7 To assess adherence to MGE treatment.

To analyze objective 2.2.7, we will summarize the percent of pills taken at the end of every 4 week period i using the formula:

Percent of pills taken_i =

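### A 30-day MGE supply does not cover the permitted visit window, so an adherent patient can be off drug for up to 5 days when Week 8 phenolics, cytokines and growth factors are drawn

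*Combined protocol and SAP*

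**What the plan says.** **Supply.** At baseline: "Study drug (30-day supply) will be provided to participant by the RN" (6.3.1.4). At follow-up visits the nurse is to "provide 30-day supply of MGE at prescribed dose level" (6.3.2.2).

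**Visits.** Week 4 is day 28 ± 3 (6.1, footnote j). After that: "Study appointments at Week 8 and after will be scheduled 28 days after the prior appointment, ± 7 days" (6.1, footnote k).

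**Sampling.** "Total and component phenolics will be measured from blood and urine at baseline, 4 weeks, and 8 weeks if the patient remains on MGE" (10.1). Cytokines and growth factors are drawn at the same visits (10.2).

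**Analysis.** Section 12.2.2 fits a mixed model with "phenolic level as the outcome and time (baseline, 4, and 8 weeks) as a fixed effect" and subject as a random effect. Section 12.2.3 does the same for each cytokine or growth factor. Neither model has a term for time since last dose.

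**Checks on exposure.** "Phone contact will occur 2 weeks after each clinic visit (± 3 days) until the Week 8 visit is complete" (6.1, footnote h). The schedule also has a pill diary and an adherence assessment at Week 8, and the nurse counts capsules at follow-up visits. Accountability logs record "quantities dispensed to patients, including lot number, date dispensed, patient identifier number, protocol number, dose, quantity returned" (9.1). Section 12.2.7 scores adherence against a fixed 28 days.

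**Washout.** "The washout period for this drug is 24 hours" (6.2.1), stated when defining which late toxicities count as DLTs.

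The visible text provides no overage, no carry-over of unused capsules and no resupply between visits. The pill diary (Appendix H) and the physician order form (Appendix P) are separate attachments that were not available.

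**The concern.** The dispensed quantity covers 30 days, while the visit window runs to 35. A site and a patient who both follow the plan exactly can therefore reach Week 8 with the capsules used up, and the research blood and urine are drawn at that same visit. Objectives 2.2.2 and 2.2.3 ask about change while on MGE. The models see only the label Week 8, so a sample taken after the supply ran out enters as an ordinary on-treatment value. If the analytes move back toward baseline once dosing stops, the estimated Week 8 change is diluted. The same supply mismatch recurs at every later four-weekly visit, although no phenolic or cytokine samples are scheduled then.

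**Working it through.** **Inputs.** Supply 30 days (6.3.1.4, 6.3.2.2). Week 4 on days 25 to 31 (28 ± 3, footnote j). Interval from Week 4 to Week 8 of 21 to 35 days (28 ± 7, footnote k). Two capsules per day at Level 1 up to ten at Level 5 (6.2). The plan states no figure of its own to reproduce.

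**1. Gap at Week 8, leftovers returned.** Gap = max(0, interval − 30).
- Interval 21 to 30 days: 0.
- Interval 31, 32, 33, 34, 35 days: 1, 2, 3, 4, 5 days.

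This assumes a full day's dosing from the new supply on the dispensing day. If dosing from it starts the next day, each gap is one day shorter: 0 to 4 full days. A morning visit on day 31 is then only about 12 hours after the last twice-daily dose.

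**2. Gap at Week 8, leftovers kept.** With Week 4 on day *d* and a 35-day interval, gap = 5 − max(0, 30 − *d*).

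| Week 4 on day | 25 | 26 | 27 | 28 | 29 | 30 | 31 |
|---|---|---|---|---|---|---|---|
| Gap (days) | 0 | 1 | 2 | 3 | 4 | 5 | 5 |

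Keeping leftovers shortens the gap but removes it at a 35-day interval only if Week 4 was on day 25.

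**3. Gap at Week 4.** A day-31 visit gives 31 − 30 = up to 1 day past the baseline supply. DLT assessment covers 28 days plus day 29, so this shortfall comes after it.

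**4. Would the phone call catch it?** The call comes 14 ± 3 = 11 to 17 days after Week 4, which is at least 30 − 17 = 13 days before the supply ends. It cannot.

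**5. Would the adherence score catch it?** I read Dose Level in the 12.2.7 formula as capsules per day. At Level 1 the denominator is 2 × 28 = 56, and the percentages are the same at every level.
- 30-day supply, seen on day 35, none returned: (56 − 0)/56 = 100%. The returned-pill score shows no gap.
- 30-day supply, on time, fully adherent, 60 − 56 = 4 returned: 52/56 = 93%.
- 35-day supply, on time, fully adherent, 70 − 56 = 14 returned: 42/56 = 75%.

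With (dispensed − returned)/(daily capsules × actual days):
- 35-day supply, on time: (70 − 14)/(2 × 28) = 100%.
- 30-day supply, seen on day 35: 60/(2 × 35) = 86%, which flags the gap.

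**6. Scale of dilution (illustration only).** Suppose one sample reads fully at baseline, all true changes are equal and nobody leaves before Week 8. The mean Week 8 change then falls by 1/n: 1/30 = 3.3% with six patients at each of five levels, and 1/15 = 6.7% with three per level. If change is instead proportional to dose, the fall depends on the affected patient's level. With six per level it is 1/90 = 1.1% (Level 1) to 5/90 = 5.6% (Level 5). With three per level it is 1/45 = 2.2% to 5/45 = 11.1%. Partial clearance gives less.

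**The case against.** - **Other sources of variation in exposure are larger.** After day 28, treatment may be held for any reason and restarted within 21 days (6.5.1.2), and no dose-to-sample interval is set for blood or spot urine (10.1). Nominal-time models already pool such samples. This stands: the supply mismatch is a narrow case of a wider issue, and the fix below does not reach the rest. A hold is a clinical or patient decision, however, whereas this gap is created by the dispensing rule and is avoidable.
- **Staff would notice.** An adherence assessment and a pill count take place at Week 8 itself, and the diary and accountability logs could show when capsules ran out. This also stands, so it would be wrong to infer that the gap is undetectable. What is missing is any link from those records to 12.2.2 or 12.2.3.
- **Appendix H or P may deal with quantity or resupply.** Possibly, and nothing visible forbids early resupply. The protocol body still says 30 days twice.
- **Little depends on it.** Week 8 change is a secondary estimate with no decision rule, and the Week 4 contrast serves the same objectives. This keeps the point minor.

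A reader might go further and infer that the Week 8 results are known to be biased, since a gap of several days exceeds the 24-hour washout. The documents do not support that. The figure is given for attributing toxicity, and no clearance time is stated for phenolics or recovery time for cytokines.

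**Conclusion.** The mismatch is real and minor. A fully adherent patient seen 31 to 35 days after Week 4 can be off drug for up to 5 days when the Week 8 research samples are taken. The limit is 4 full days if the new supply is started the day after dispensing, and lower if leftovers are kept. A day-31 Week 4 visit can fall up to 1 day past the baseline supply. Visits within 30 days of the previous one are unaffected.

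Any bias in the Week 8 change would be toward no effect, provided the analytes return toward baseline off drug. Its size cannot be estimated, because neither the share of late visits nor clearance is given; the dilution percentages show scale, not a likely bias.

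A reader might also infer that dose escalation is compromised. It is not: DLTs are assessed over the first 4 weeks plus one day, which the baseline supply covers, so the DLT and MTD outcome is essentially unaffected.

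**What to change.** Dispense a 35-day supply at baseline and at every visit (6.3.1.4, 6.3.2.2). This covers the latest permitted Week 4 visit (day 31) and the longest later interval (35 days), so the maximum gap is 0.

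At the same time, change the 12.2.7 formula to (pills dispensed − pills returned) / (daily pills × actual days in the interval). The two changes belong together, because the larger supply would otherwise depress the adherence score of on-time patients to the 75% shown above.

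**Cost.** Five extra days at 2, 4, 6, 8 or 10 capsules per day is 10, 20, 30, 40 or 50 more capsules per dispensing at Levels 1 to 5, plus a one-line formula edit.

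**Partial alternative.** Keep 30 days and cap the late side of the Week 8 window at +2 days (28 + 2 = 30). This needs no extra drug but gives up some scheduling flexibility. It does not cover a day-31 Week 4 visit or the later visits.

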6.4 General Concomitant Medication and Supportive Care Guidelines

Patients should receive *full supportive care*, including transfusions of blood and blood products, antibiotics, antiemetics, etc., as clinically indicated. Antiinflammatory or narcotic analgesics may be offered as needed. Medications considered necessary for the patient's well-being may be given at the discretion of the managing physician, i.e., chronic treatments for concomitant medical conditions, as well as agents required for life-threatening medical problems, etc. The reason(s) for treatment, dosage, and dates of treatment should be recorded on the flow sheets.

Participants on warfarin should have their INR checked within 2 weeks of starting MGE to ensure there is no clinically significant interaction. Further blood work to monitor warfarin levels are at the discretion of the treating physician per usual care.

6.5 Duration of Therapy

In the absence of treatment delays due to adverse events, treatment may continue until one of the following criteria applies:

- Disease progression, either by standard imaging or clinical parameters per the judgment of the treating physician,
- Intercurrent illness that prevents further administration of treatment,
- Unacceptable adverse event(s),
- Patient decides to withdraw from the study, or
- General or specific changes in the patient's condition render the patient unacceptable for further treatment in the judgment of the treating physician.

6.5.1 Missed doses

If a dose of MGE is missed, the patient will be instructed to take their next dose as scheduled. Missed doses should not be added to the next dose.

6.5.1.1 Missed doses during first 28 days

If the patient is unable to take their dose of MGE for more than 7 consecutive days due to unforeseen circumstances unrelated to drug toxicity, then the subject will not be evaluable for the primary outcome and will be removed from the study. Participants who come off study prior to 28 days for reasons other than toxicity will be evaluated for DLT during the washout period (24 hours, per section 6.2.1).

6.5.1.2 Missed doses after first 28 days

If treatment must be held for any reason, it must be restarted **within 21 days** or the patient will be removed from the study.

6.6 Duration of Follow Up

Patients removed from the study for unacceptable adverse events will be followed until resolution or stabilization of the adverse event. Patients who are removed or withdraw from the study for any reason other than toxicity will be followed for vital status only after the 24 hour washout period. Patients will be followed every 6 ± 2 weeks until death for monitoring survival study endpoints.

7.0 Measurement of Effect

Although response is not the primary endpoint of this trial, patients with measurable disease will be assessed by the treating physician, based on the clinical radiologic report and clinical status, per usual care. For the purposes of this study, patients will be reevaluated with imaging 8 weeks (± 7 days) after study initiation and then every 12 weeks (± 28 days) while on MGE.

7.1 Definitions

Evaluable for toxicity (primary outcome): All patients will be evaluable for toxicity from the time of their first treatment with MGE. Per section 6.5.1, patients who miss 7 consecutive days of treatment in the first 28 days for reasons other than toxicity are not evaluable and will be removed from the study and replaced.

Inevaluable for objective response: When no imaging/measurement is done at all at a particular time point, the patient is not evaluable (NE) at that time point.

Measurable disease: Measurable lesions are defined as those that can be accurately measured in at least one dimension (longest diameter in the plane of measurement is to be recorded) with a minimum size of 10 mm by CT scan, 10 mm caliper measurement by clinical exam, or 20 mm by chest X-ray.

Non-measurable lesions: Non-measurable lesions include: bony metastases, leptomeningeal disease, ascites, pleural or pericardial effusion, inflammatory breast disease, lymphangitic involvement of skin or lung, abdominal masses or organomegaly identified by physical exam that is not measurable by reproducible imaging techniques.

Progression-Free Survival is defined as the duration of time from the start of treatment to the time of progression or death. Patients will be followed until disease progression and death.

Overall Survival is defined as the duration of time from the start of treatment to date of death.

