At the time of sacrifice, various organs (heart, lung, liver, kidney, spleen and brain) were removed and weighed and the organ weights of mice treated with each dose of MGE were compared to the untreated control group. A portion of each organ was fixed in formalin, sectioned and stained with H & E. for assessment by a veterinary pathologist. In addition. the heart and kidney were assessed by echocardiography and radioimmunoassay of urinary proteins, respectively, as a further measure of heart and renal function. There was no difference in the weight or structure of the hearts of mice treated with increasing doses of MGE. Cardiac parameters including ejection fraction, fractional shortening, cardiac output, stroke volume and heart rate were all similar in mice treated with MGE compared to untreated Control mice. There was no difference in the weight or structure of the lungs of mice treated with MGE compared to the untreated control mice. The weight of the livers of mice treated with the two lowest MGE (0.25 and 0.5 mg phenolics/mouse/day) and the highest MGE (2.0 mg phenolics/mouse/day) concentrations were no different than the weight of the livers of the untreated mice. However, the weight of the livers of mice in the 1.0 mg phenolics/mouse/day) were slightly increased compared to the control. Spleen weight of mice treated with MGE was not significantly different than untreated control mice and the spleens of mice were generally within normal limits with one mouse in the highest MGE treatment group having some extra medullary hematopoiesis. The weight of the brains of mice treated with MGE was not significantly different than untreated mice. The brains were subdivided into four regions—cortex, cerebellum, hypothalamus and brainstem. All brain regions examined were within normal limits.

Conclusions from toxicity studies and corresponding clinical doses:

Little toxicity was observed at any of the doses tested. Therefore, the level of phenolics used to treat the mice suggests that this level of phenolics and corresponding numbers of capsules will likely be tolerated by patients. However, based upon patient compliance, a recommended dose range for patients would include 2, 4, 6, 8 and 10 capsules/day (corresponding to approximately 5, 9, 14, 18 and 23 mg phenolics/kg/day).

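### DLT evaluability tests only for a run of consecutive missed days and sets no minimum cumulative exposure, so the MTD can be biased upward

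*Combined protocol and SAP*

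**What the plan says.** The primary outcome is DLT at 4 weeks (5.1.1), and the 3+3 rules in 6.2.1 and 12.1 act on the number of patients with a DLT at each level.

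- **Who counts.** Section 7.1 starts from "All patients will be evaluable for toxicity from the time of their first treatment with MGE". Its one exception tied to dose received is that "patients who miss 7 consecutive days of treatment in the first 28 days for reasons other than toxicity are not evaluable"; such patients are removed and replaced.
- **The parallel rule.** Section 6.5.1.1 applies when doses are missed for more than 7 days in a row "due to unforeseen circumstances unrelated to drug toxicity, then the subject will not be evaluable for the primary outcome".
- **Holds.** Section 6.2.2 says "MGE can be held for up to 7 days in the first month and for up to 21 days subsequently, as described in Section 6.5.1". It also rules out dose modification on study.
- **Early leavers.** Section 6.5.1.1 adds "Participants who come off study prior to 28 days for reasons other than toxicity will be evaluated for DLT during the washout period". It does not say whether they then count as DLT-free or are replaced.
- **Adherence.** Diaries, pill counts and a week-2 contact are planned (6.1, 6.3.2). Under 12.2.7 they feed a secondary summary of percent of pills taken by dose level. No section links them to the DLT count or the escalation decision.

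**The concern.** A 3+3 design reads each DLT-free patient as evidence that the assigned dose was tolerated for 28 days. A patient who took little of that dose gives little such evidence, yet fills a place in the cohort and helps satisfy the 0-of-3 or 1-of-6 condition. With only 3 to 6 patients per level, one such patient can change an escalation decision, and a secondary adherence table produced later cannot undo it.

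The rule looks only at the length of one gap. It sets no limit on total missed days and does not say how partial daily doses are treated. Doses missed because of toxicity never make a patient inevaluable, so someone who skips doses for symptoms short of the DLT definition also stays in the count as DLT-free.

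**Working it through.** **The plan's own figures.** Five levels (6.2) at up to 6 patients each (12.1) give 5 × 6 = 30. Two DLTs in the first two patients give 2. Both match the enrolment range in 12.3. The plan states no operating characteristics, adherence rate or dose-toxicity curve.

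**Lowest exposure that stays evaluable**, with day 1 dosed:

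- Under 7.1 (7 missed days disqualify): dosing on days 1, 8, 15 and 22 leaves four gaps of 6 days. That is 4/28 = 14.3%.
- Under 6.5.1.1 (more than 7 disqualify): dosing on days 1, 9, 17 and 25 leaves gaps of 7, 7, 7 and 3 days. Again 4/28 = 14.3%.

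At Level 5 (10 pills a day) this is 4 × 10 = 40 of 280 assigned pills. A fully adherent Level 1 patient takes 2 × 28 = 56.

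**Chance of passing one level.** P(pass) = P(0 of 3) + P(1 of 3) × P(0 of next 3). The inputs are assumptions: a true DLT rate of 0.33 at the full dose, and in each group of three one under-dosed patient with rate r.

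- P(0 of 3) = 0.67² × (1 − r)
- P(1 of 3) = 0.67² × r + 2 × 0.33 × 0.67 × (1 − r)

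| r | P(0 of 3) | P(1 of 3) | P(pass) |
|---|---|---|---|
| 0.33 (all fully dosed) | 0.301 | 0.444 | 0.434 |
| 0.20 | 0.359 | 0.444 | 0.518 |
| 0.10 | 0.404 | 0.443 | 0.583 |
| 0.05 | 0.426 | 0.443 | 0.615 |

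**Whole trial** (100,000 simulated 3+3 trials per scenario; DLT risk assumed proportional to dose taken; under-dosed patients at 4/28 of the dose):

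- Assumed DLT rates 0.05, 0.10, 0.20, 0.35, 0.50 by level. With 0% and 20% under-dosed, the mean selected level is 2.67 and 2.99. The chance of selecting a level with a true rate above 1/3 is 0.204 and 0.326.
- Assumed DLT rates 0.01, 0.02, 0.03, 0.05, 0.08. Even with 33% under-dosed, the mean selected level moves only from 4.82 to 4.90.

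**The 7-day limits side by side.** A patient who misses exactly 7 consecutive days for a non-toxicity reason is inevaluable under 7.1 and evaluable under 6.5.1.1. Section 6.2.2 could mean 7 days in total, which would give (28 − 7)/28 = 75%. However, it refers to 6.5.1, which counts consecutive days, and it concerns holds, not missed doses.

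**The case against.** The strongest reply is that the size is unknown and may be nil. The expected adverse events are minimal (8.1), the mouse studies showed little toxicity (1.2), and no dose-limiting toxicity was seen with a related product (1.3). With toxicity that low, the simulation barely moves. There is also partial protection: an attributable event leading to permanent discontinuation is a DLT (6.2.1), and adherence is checked at weeks 2 and 4. All of this stands as a limit on size. It does not close the gap, because the DLT definition does not catch intermittent dosing and no consequence follows from the adherence checks.

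Three stronger readings are tempting, and the documents do not support them.

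- A reader might infer from "based upon patient compliance, a recommended dose range for patients would include 2, 4, 6, 8 and 10 capsules/day" that under-dosing will be concentrated at the top levels. In context, that sentence explains why the range stops at 10 capsules when the mouse doses corresponded to 5 to 42. Nothing says adherence falls from Level 1 to Level 5.
- A reader might infer that a Level 5 patient taking 5 of 10 pills every day is certainly evaluable. Section 6.5.1.1 speaks of inability to take the dose, and 6.2.2 allows no dose modification, so the status of a partial dose is unclear.
- A reader might take 6.2.2 as already capping missed days at 7 in total. Its cross-reference and its subject do not settle that.

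**Conclusion.** The point holds in conditional form. Followed exactly, 6.5.1.1 and 7.1 let a patient dosed on 4 of 28 days count as DLT-free at the assigned level. If DLT risk rises with dose and some patients are under-dosed, the MTD can be biased upward. A reader might infer that it will be, but the documents give neither an adherence rate nor a dose-toxicity curve, so that is not established.

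The rise from 43% to between 52% and 62% rests on the assumed 33% rate, one under-dosed patient in every three, and a reduced rate of 20% to 5%. With very low toxicity or good adherence the effect is negligible.

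Separately, 7.1 and 6.5.1.1 contradict each other at exactly 7 days, and 6.2.2 is ambiguous between a total and a consecutive limit.

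**What to change.** Define a DLT-evaluable set in 7.1 and use it in 6.2.1 and 12.1. The criterion governs only who counts in the DLT denominator.

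- A patient with a DLT always counts.
- A patient without a DLT counts only after taking a pre-stated minimum share of assigned pills in days 1 to 28, by diary and pill count. An example is 75%, equal to 21 of 28 days; the sponsor should confirm the figure. State how partial daily doses enter the share.
- Patients below the minimum for non-toxicity reasons are replaced under the existing rule.
- Patients below it because of attributable symptoms are not counted as DLT-free by default. The sponsor states in advance how they count.

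A floor limits the bias without removing it. If risk is proportional to dose, the full-dose rate is 0.33 and each patient has a 33% chance of being under-dosed, P(pass) is 0.629 when those patients take 4/28 of the dose and 0.489 when they take 75%, against 0.434 with full dosing.

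The sponsor must separately reconcile the limits in 6.2.2, 6.5.1.1 and 7.1. No hold or removal rule is proposed here.

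**Cost.** Mostly wording, since the adherence data are already collected. There are two further items.

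- The maximum of 30 has no room for replacements. If 10%, 20% or 33% of patients were replaced (assumed), 30/(1 − d) gives 34, 38 or 45.
- The 12.2.7 formula must count twice-daily pills. If its dose term is the level number, a Level 1 patient returning 28 of 56 pills scores (28 − 28)/28 = 0% when the true figure is (56 − 28)/56 = 50%. It must also allow for the 30-day supply (6.3.1.4): a fully adherent Level 1 patient returns 4 of 60 pills after 28 days, and (56 − 4)/56 = 93%.
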